5 GENERAL STATISTICAL CONSIDERATIONS

The primary analysis for the efficacy endpoints will be conducted using data collected through the 12-week treatment period. Data will be cleaned and locked prior to conducting the primary analysis.

The final analysis will be conducted after all subjects have completed their Week 16 or end of study (EOS) visit and after all study data is cleaned and locked.

SAS® version 9.4 or higher will be used for statistical analyses, tabulations, and graphical presentations.

In general, descriptive summaries will be presented by treatment groups (placebo and ESK-001 dose levels) and overall, for values at each visit. The descriptive summary for continuous variables will also be provided for the change from baseline and, if appropriate, for the change from week 12 to week 16. Summaries of continuous variables will include the number of subjects (N), mean, standard deviation (SD), median, Q1, Q3, minimum, and maximum. If there are variables with highly skewed distribution (e.g. log-normal distribution), then the geometric mean and %CV will also be reported in descriptive summaries. Inferential analysis for those variables may be performed after log-transformation as deemed appropriate. Descriptive summaries for categorical variables will include the number and percentage of subjects. Unless otherwise stated, denominators for percentages will be the number of subjects in the analysis population.

Between-group comparisons will focus on the comparative performance of a single ESK-001 dose versus placebo. All statistical tests will be conducted at a 2-sided significance level of 0.05. The corresponding p-values and two-sided 95% confidence intervals will be reported.

In general, baseline is defined as the last non-missing value prior to the first dose date and time. For subjects randomized but not dosed, the last non-missing value prior to the randomization date will be used as baseline. For any additional considerations, refer to each specific data section for details.

In general, efficacy data and other non-safety data will be presented by analysis visits as defined by the analysis visit window. Data collected at unscheduled or early termination (ET) visits will also be mapped to analysis visits as defined in [Appendix B](#). If a value does not fall within an analysis window, it will not be included in the summary analysis or comparative analysis.

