5.1 Analysis Populations

The following analysis populations are defined in this study:

- Modified Intent-to-Treat (mITT) Population: All randomized subjects who received at least one dose of study drug, with analyses conducted according to the assigned treatment. This will be the analysis population used for the primary efficacy analysis at Week 12.
- Intent-to-treat (ITT) Population: All randomized subjects, regardless of whether they receive study drug, with analyses conducted according to the assigned treatment.
- Per-protocol (PP) Population: All subjects in the ITT population who have received at least one dose of study drug as assigned, have both baseline and at least one post-baseline PASI score, and have no important protocol deviations (IPD) which may affect key primary and secondary efficacy endpoints in the treatment period.
- Safety Analysis Population: All randomized subjects who receive at least one dose of study drug with analyses conducted by actual treatment received.
- PK Analysis Population: All randomized subjects who receive at least 1 dose of ESK-001 and have at least one non-missing PK concentration with analysis conducted by actual treatment received.

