5.3 Missing Data

In general, missing data will not be imputed unless specifically stated in this SAP. Refer to [Section 7](#) on handling of missing data for responder analyses.

Handling of Missing Data:

For data collected with start and end dates such as medical history and concomitant medications, the following may be applied to missing or partial dates:

- Start Dates:

- If day is missing, then impute it to be the start of the month (eg, 01MMYYYY); except if the month and year is equal to the first dose date month and year then impute the day to be the same day as the first dose date.
- If month is missing, then impute it to be the start of the year (eg, 01JANYYYY), except if the year is equal to the first dose date year then impute the day and month to be the same as the first dose date.
- If year is missing, then do not impute.
- End Dates:
 - If day is missing, then impute it to be the end of the month (eg, 31MMYYYY), except if the month and year is equal to the last assessment date month and year then the day should be imputed to the last participation date day.
 - If month is missing, then impute it to be the end of the year (eg, 31DECYYYY), except if the year is equal to the last participant date year then the day and month should be imputed to the last participant date day and month.
 - If year is missing, then do not impute.
- For all other type of dates:
 - If only day is missing, then impute it to be the start of the month (eg, 01MMYYYY).
 - If month and day are missing, then impute it to be the start of the year (eg, 01JANYYYY).
 - If year is missing, then do not impute.

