7 EFFICACY ANALYSES

All efficacy analyses will be conducted using the mITT Analysis Population. A sensitivity analysis using the ITT or PP analysis set may be performed as appropriate.

The primary and secondary endpoints are based on the efficacy response at the end of treatment (ie. Week 12).

In general, for responder type analyses, the difference in the proportion of subjects between two treatment arms at Week 12 or other timepoints (eg. Week 4, 8, if applicable) and the corresponding two-sided 95% CI will be calculated using the Fisher's exact test or the Chi-squared test depending on the number of observations (if cell counts are less than 5 then use Fisher's). A test of significance for the difference in proportion between two treatment groups will be performed using the Cochran Mantel-Haenszel (CMH) test adjusting for randomization stratification factors and the corresponding two-sided p-value will be presented.

A non-responder imputation will be applied to responder analyses in which subjects who drop out of the study before Week 12 will be considered as a non-responder at the week 12 visit. No imputation will be applied at any other post-baseline visits. [REDACTED]

For continuous efficacy measurements or scores, the treatment difference in the change from baseline between each active treatment and placebo will be compared using an ANCOVA model, with treatment group, visit and randomization stratification factors as fixed effects and baseline measure as a covariate. An unstructured covariance matrix will be used to model the correlation among repeated measurements (if convergence issues are encountered then compound symmetry covariance matrix will be used instead). Within-group least-squares (LS) means, standard errors (SEs), 2-sided 95% CIs, and p-values will be presented for Week 12 and other timepoints, if applicable.

Some efficacy analyses may also be presented by select subgroups of interest such as baseline PASI, age, BMI, race, gender and prior biologic use categories (refer to [Section 5.2](#)). However, given the small sample size, test for statistical significance will not be conducted for subgroup analyses.

[REDACTED]

[REDACTED]

[REDACTED]

[REDACTED]

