7.1 Primary Efficacy Analyses

7.1.1 *Psoriasis Area and Severity Index*

Disease activity will be assessed by the Psoriasis Area and Severity Index (PASI) which derives a score for the severity of psoriatic lesions by evaluating erythema, induration, and scaling in each of 4 body regions, as detailed in [Appendix C](#).

The primary endpoint is the proportion of subjects achieving $\geq 75\%$ reduction in PASI score (PASI-75) at Week 12.

The proportion of subjects achieving PASI-75 will be summarized for each post-dose timepoint by treatment group. The primary efficacy analysis will compare the proportion of subjects achieving PASI-75 at Week 12 between each active treatment and placebo using the CMH method as described in [Section 7](#). This analysis will be repeated at Weeks 4 and 8.

The absolute value, change and percent change from baseline in PASI score will be summarized using descriptive statistics by timepoint and treatment group. Additionally, the difference in the change from baseline between each active treatment and placebo will be assessed using ANCOVA model as described in [Section 7](#). The analysis will be repeated with percent change from baseline as the dependent variable. Estimates of least-squares (LS) means, SEs, 2-sided 95% CIs and p-values will be presented by treatment group for Weeks 4, 8 and 12.

Absolute PASI scores and the proportion of subjects achieving PASI-75, PASI-90, PASI-100, PASI-50 will also be plotted over time by treatment. The proportion of subjects achieving PASI-50, PASI-75, PASI-90 and PASI-100 at Week 12 by treatment will be presented using a bar chart. The percent reduction in PASI at Week 12 for each individual subject will be presented by waterfall plot. Each treatment group will be presented on a separate plot.

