7.4 Physician's Global Assessment

Efficacy will also be assessed by the static Physician's Global Assessment (sPGA) and the scoring system is presented in [Appendix D](#). The frequency and percentage of subjects for each discrete sPGA score (0 through 5) will be summarized by timepoint and treatment group. The proportion of subjects who achieve a sPGA response (defined as sPGA score of "0" ("cleared") or "1" ("minimal")) will be summarized for each post-dose timepoint by treatment group. The adjusted treatment difference in proportion of subjects with a sPGA response of 0 or 1 for each active treatment compared to placebo, its associated 95% CI, and two-sided p-value will be presented for Week 4, 8 and 12 using the CMH method.

Bar charts of the proportion of subjects with the following sPGA scores will be plotted by treatment for each visit: 0, 0/1, 1, 2, 3, 4, 5.

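### Dropouts count as non-responders at Week 12 but are not imputed at Weeks 4 and 8, so the earlier PASI-75 and sPGA 0/1 tests rest only on patients with a value at that visit

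*SAP*

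**What the plan says.** SAP Section 7 has two rules for responder endpoints. At Week 12, "subjects who drop out of the study before Week 12 will be considered as a non-responder at the week 12 visit". Elsewhere, "No imputation will be applied at any other post-baseline visits". Section 5.3 sets the same default, "In general, missing data will not be imputed unless specifically stated in this SAP", and refers to Section 7 for responder analyses.

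The earlier visits carry inference as well as description. After the Week 12 PASI-75 comparison of each active arm with placebo, Section 7.1.1 adds: "This analysis will be repeated at Weeks 4 and 8". It also plots PASI-50, 75, 90 and 100 response over time. In Section 7.4 the sPGA 0/1 difference, confidence interval and p-value "will be presented for Week 4, 8 and 12 using the CMH method".

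The efficacy population is mITT: "All randomized subjects who received at least one dose of study drug, with analyses conducted according to the assigned treatment" (Section 5.1). Section 5 says that, unless otherwise stated, "denominators for percentages will be the number of subjects in the analysis population". Section 5 also maps early-termination (ET) assessments to analysis visits through the Appendix B windows.

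**The concern.** A responder test needs a yes or no for each patient. A dropout with no value in the Week 4 or Week 8 window, and no imputation, has neither and is left out of that visit's CMH table. At Week 12 the same patient enters as a failure.

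Three things follow.

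- The Week 4 and 8 tests compare patients still observed, not the randomized and dosed groups. If an active arm and placebo lose different numbers or kinds of patients, the comparison can be biased either way.
- Consecutive visits follow different missing-data rules. If the plotted rates are observed-case, part of any change between Week 8 and Week 12 is a change of denominator.
- If the default percentage denominator applies to the tables, dropouts stay in the tabulated rate while the test beside it omits them. The SAP does not say which set governs.

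At stake is how early response is read in a study with five doses and placebo. The primary result is not at stake.

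**Working it through.** **Inputs.** 35 patients per arm, two-sided 0.05, 60% against 10% PASI-75 (SAP Section 4). Windows from SAP Appendix B, Table 2: Week 2 is days 12–21, Week 4 is days 22–42, Week 8 is days 43–70. ET timing after leaving the study: 2 weeks ± 7 days (Protocol 7.3). Neither document gives a dropout rate or a Week 4 or 8 response rate, so all dropout figures below are assumptions.

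**1. The plan's own figure.** Pooled proportion (0.10 + 0.60)/2 = 0.35. Null SE = √(2 × 0.35 × 0.65/35) = 0.1140. Alternative SE = √((0.09 + 0.24)/35) = 0.0971. Power = Φ((0.50 − 1.96 × 0.1140)/0.0971) = Φ(2.85) = 99.8%. Exact enumeration with Fisher's test gives 99.5%. The stated minimum of 99% is reproduced. It concerns Week 12, so this point does not touch it.

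**2. Who is missing at Weeks 4 and 8.** Place the ET visit at leaving day + 14:

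| Leaves on day | ET falls on day | Mapped to | Absent from |
|---|---|---|---|
| 1–7 | 15–21 | Week 2 | Weeks 4 and 8 |
| 8–28 | 22–42 | Week 4 | Week 8 |
| 29–56 | 43–70 | Week 8 | neither, through ET |

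The ± 7 days blurs these boundaries. A patient who skips the ET visit is absent from every later window until the Week 12 rule applies. The affected group is therefore early leavers and patients who skip ET, not all dropouts.

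**3. Size within one arm.** With r responders, n = 35 and m absent, the observed-case rate is r/(n − m) and the non-responder-imputed rate is r/n. The gap is r × m/(n(n − m)). With r = 18:

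| m absent | Observed cases | Imputed | Gap (points) |
|---|---|---|---|
| 1 | 18/34 = 52.9% | 51.4% | 1.5 |
| 2 | 18/33 = 54.5% | 51.4% | 3.1 |
| 4 | 18/31 = 58.1% | 51.4% | 6.6 |
| 6 | 18/29 = 62.1% | 51.4% | 10.6 |
| 7 | 18/28 = 64.3% | 51.4% | 12.9 |

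**4. Size of an active-versus-placebo difference.** Borrow 60% and 10% as the rates among patients with data. The observed-case difference is then 50 points whatever the dropout. With dropout fractions a (active) and b (placebo), the imputed difference is 0.60(1 − a) − 0.10(1 − b):

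- a = b = 5%: 57.0% − 9.5% = 47.5 points
- a = b = 20%: 48.0% − 8.0% = 40.0 points
- a = 20%, b = 5%: 48.0% − 9.5% = 38.5 points
- a = 5%, b = 20%: 57.0% − 8.0% = 49.0 points
- a = 0, b = 20%: 60.0% − 8.0% = 52.0 points

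The imputed difference minus the observed-case difference is 0.10b − 0.60a, so its sign depends on the dropout pattern. These are gaps between two analyses. They are not bias against a known truth, because the leavers' outcomes are unknown.

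**5. Effect on the tests.** With 20% lost from each arm, the formula in step 1 gives 98.9% power on observed cases (28 per arm, 60% against 10%) and 97.6% with imputation (35 per arm, 48% against 8%).

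**The case against.** The strongest reply is that Weeks 4 and 8 are supportive, all primary and secondary efficacy endpoints are at Week 12, and a prespecified observed-case analysis at supportive visits is legitimate. That stands, and it limits the weight of the point. It does not settle the change of rule between consecutive visits or the unstated denominator.

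A reader might also infer more than the documents support:

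- **That every dropout disappears at both visits.** ET mapping keeps many of them. A patient who leaves in Week 3 (days 15–21) and attends ET is seen on days 22–42, inside the Week 4 window, and is missing only at Week 8. Protocol 7.2 also asks patients who stop study drug to stay for all assessments.
- **That SAP Section 5 excludes missing values.** Its sentence, "If a value does not fall within an analysis window, it will not be included in the summary analysis or comparative analysis", covers values that exist outside a window. The exclusion follows instead from barring imputation in Section 7.
- **That the Week 4 and 8 tables are certainly completers-only rates.** Under the default mITT denominator they could be 18/35 whatever the dropout. The doubt is about the test set and its agreement with the table.
- **That the doses are formally compared with each other on selected patients.** Dose-versus-dose tests are at Week 12 only (SAP 7.2.1). Earlier tests are against placebo.
- **That the bias favors the drug.** Its direction depends on which arm loses patients and why.

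Text directly after the Section 7 sentence is blacked out. It is not a gap in the plan, and it cannot be assumed to reverse a visible rule that has no conditions.

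**Conclusion.** The point holds for the Week 4 and 8 responder tests. Dropouts with no in-window value are omitted from them and then return as failures at Week 12, and the SAP does not say whether the tabulated rates use the same patients as the tests. In the single-arm example the gap is 1.5 points with 1 of 35 absent and 10.6 points with 6 absent. The dropout numbers, the 18 responders and the use of Week 12 planning rates at earlier visits are all assumptions. Actual absence will be lower where patients attend ET.

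The Week 12 primary and secondary endpoints and the stated power are unaffected. This is a modest but worthwhile improvement to supportive analyses.

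**What to change.** In SAP Section 7, replace the sentence that bars imputation at other visits with:

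> At Weeks 4 and 8 (and any other scheduled visit before Week 12 with a responder summary), a subject who has dropped out of the study and has no observed value in that visit's analysis window, including a mapped ET value, is a non-responder at that visit.

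State that tests, tables and plots at these visits use the mITT denominator, and keep observed-case rates as a supportive table. The condition on observed values matters: without it, a patient leaving on day 40 with an ET visit on day 54 would have a real Week 8 value and also be an imputed failure.

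The cost is one sentence and a denominator statement before the SAP is finalized, with no new data. The Week 4 and 8 response rates become slightly lower. The Week 12 rule stays as written.

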10.3.2. Secondary Efficacy Endpoints

Similar analyses as in the primary efficacy analyses will be performed to compare any two active arms.

The proportion of patients in each treatment group and placebo with sPGA categories 0 or 1 (cleared or minimal) at Week 12 will be compared using the Cochran-Mantel-Haenszel test adjusting for stratification factors.

The proportion of patients in each treatment group and placebo with response rate in PASI-50, 90, and 100 at Week 12 relative to baseline will be compared using methods similar to those used for PASI-75.

Change in percent BSA at Week 12 relative to baseline will be performed using ANOVA or analogous nonparametric methods.

Change from baseline in DLQI at Week 12 relative to baseline will be performed using ANOVA or analogous nonparametric methods.

The proportion of patients in each treatment group and placebo with $\geq 75\%$ improvement in PASI Week 12 relative to baseline will be compared using the Cochran-Mantel-Haenszel test adjusting for stratification factors.

No adjustments for multiplicity will be performed.

Graphical methods may be used to display efficacy data.

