2 STUDY OBJECTIVES AND ENDPOINTS

Objectives	Endpoints
Primary	

To compare the Psoriasis Area and Severity Index (PASI-75) between doses of ESK-001 and placebo after 12 weeks of treatment	
Proportion of patients with moderate to severe psoriasis achieving $\geq 75\%$ reduction in PASI score at 12 weeks between doses of ESK-001 and placebo
Secondary	

To assess the safety and tolerability of ESK-001 dose in moderate to severe psoriasis patients	
Incidence of treatment-emergent adverse events (TEAEs) and serious adverse events (SAEs)

To characterize the pharmacokinetics (PK) of ESK-001	
Plasma concentrations and PK parameters of ESK-001

To assess the response rate in static Physician's Global Assessment (sPGA) score after 12 weeks of treatment	
Proportion of patients achieving an sPGA score of "0" ("cleared") or "1" ("minimal") after 12 weeks of ESK-001 treatment compared with placebo

To assess the response rate in PASI-50, 90, and 100 score after 12 weeks of treatment	
Proportion of patients achieving PASI-50, 90, and 100 after 12 weeks of ESK-001 treatment compared with placebo

To compare the response rate in PASI-75 among ESK-001 treatments	
Proportion of patients achieving PASI-75 at 12 weeks compared among the ESK-001 treatments

To assess the effect on body surface area (%BSA) involved with psoriasis after 12 weeks of treatment	
Change from baseline in %BSA after 12 weeks of ESK-001 treatment compared with placebo

To assess the change in Dermatology Life Quality Index (DLQI)	
Change from baseline in DLQI at Week 12 in ESK-001 compared with placebo
Exploratory	

To assess the change in pruritus numerical rating scale (NRS) after 12 weeks of treatment	
Change from baseline in NRS score after 12 weeks of ESK-001 treatment compared with placebo

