7.3 Psoriasis Body Surface Area

Measurement of psoriasis body surface area (BSA) involvement is a continuous variable and estimated using the handprint method with the size of a patient's handprint representing $\sim 1\%$ of body surface area involved.

The absolute value and change from baseline in %BSA will be summarized using descriptive statistics by timepoint and treatment group. The absolute value and change from baseline in %BSA will be summarized using descriptive statistics by timepoint and treatment group. Additionally, the difference in the change from baseline between each active treatment and placebo will be assessed using ANCOVA model as described in [Section 7](#). Estimates of least-squares (LS) means, SEs, 2-sided 95% CIs and p-values will be presented by treatment group for Weeks 4, 8 and 12. The absolute value and change from baseline in %BSA over time will be plotted by treatment.

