7.5 Patient-Reported Outcomes

Quality of life (QoL) will be assessed by the following patient-reported outcomes (PRO): the Dermatology Life Quality Index (DLQI), the EQ-5D-5L, and the pruritus numerical rating scale (NRS). The two questions collected in NRS questionnaire will be assessed separated as the average itch within the past 24 hours and the worst itch within the past 24 hours. Since the EQ-5D-5L value sets used to calculate the index score are country-specific and there currently are none available for Czech Republic where some subjects are enrolled in this study, the value set for Poland will be used instead as the closest Eastern European country with available scoring instrument.

DLQI score, NRS average and worst itch scores, and the EQ-5D-5L index score are continuous variables, and the absolute value, change and percent change from baseline in each PRO assessment will be summarized using descriptive statistics by timepoint and treatment group. The absolute value, change and percent from baseline for each PRO measure will be summarized using descriptive statistics by timepoint and treatment group. Additionally, the difference in the change from baseline between each active treatment and placebo will be assessed using ANCOVA model as described in [Section 7](#). The analysis will be repeated with percent change from baseline as the dependent variable. Estimates of least-squares (LS) means, SEs, 2-sided 95% CIs and p-values will be presented by treatment group for Weeks 4, 8 and 12. The absolute value over time will be plotted by treatment for the EQ-5D-5L index score, the DLQI score, the NRS average itch and worst itch scores.

Additionally, a responder analysis will be conducted for DLQI where a responder is defined as the subject who achieved a post-baseline score of 0 or 1.

A responder analysis will also be conducted for NRS questionnaire where a responder is defined as a subject who has achieved a post-baseline itch score of < 4.

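### The SAP's repeated-measures model has no treatment-by-visit term, so as written it does not estimate the Week 12 difference defined for %BSA and DLQI

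*SAP*

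**What the plan says.** SAP Section 7 sets one model for all continuous efficacy measures: "an ANCOVA model, with treatment group, visit and randomization stratification factors as fixed effects and baseline measure as a covariate". The next sentence makes it a joint model over visits: "An unstructured covariance matrix will be used to model the correlation among repeated measurements", with compound symmetry as the fallback. For output, the section states that "p-values will be presented for Week 12 and other timepoints, if applicable".

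Sections 7.1.1 (PASI change and percent change), 7.3 (%BSA) and 7.5 (DLQI, NRS, EQ-5D-5L) refer back to this model and add no terms. Section 7.5, for example, says "the difference in the change from baseline between each active treatment and placebo will be assessed using ANCOVA model as described in" Section 7. Section 7.3 promises: "Estimates of least-squares (LS) means, SEs, 2-sided 95% CIs and p-values will be presented by treatment group for Weeks 4, 8 and 12". Sections 7.1.1 and 7.5 promise the same.

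The secondary endpoints are tied to Week 12. SAP Section 2 gives "Change from baseline in DLQI at Week 12 in ESK-001 compared with placebo" and defines %BSA after 12 weeks of treatment. Protocol 10.3.2 planned a single-timepoint comparison: "Change in percent BSA at Week 12 relative to baseline will be performed using ANOVA or analogous nonparametric methods", and the same for DLQI.

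The SAP does not list the visits that enter the model. Section 5 says "The primary analysis for the efficacy endpoints will be conducted using data collected through the 12-week treatment period". Within that limit, the analysis windows in SAP Appendix B allow Weeks 1, 2, 4, 8 and 12 for skin assessments and Weeks 2, 4, 8 and 12 for patient-reported outcomes.

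**The concern.** With treatment and visit entered only as main effects, the fitted profiles of the arms are parallel. LS means can be printed for each arm and visit, but the gap between a dose and placebo is a single parameter. It is the same number, with the same CI and p-value, under every visit label. It equals the Week 12 difference only if the effect is constant over all fitted visits, which is implausible for a change score that starts at zero.

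A programmer who follows the sentence would therefore test %BSA and DLQI on a quantity other than the one defined, under a Week 12 label. Continuous PASI, NRS and EQ-5D-5L share the model. In a five-dose Phase 2 study these estimates help to describe each dose, and they would be diluted by early visits if onset is gradual.

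**Working it through.** **The plan's own figure.** The only design figure is power for PASI-75: 10% versus 60%, 35 per arm, two-sided 0.05. With pooled variance under the null, power = Φ[(0.50 − 1.96·√(2·0.35·0.65/35)) / √((0.09 + 0.24)/35)] = Φ(2.85) = 99.8%, which agrees with the stated value of at least 99%. It does not concern the continuous endpoints.

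**What the additive model estimates.** Let d be the vector of true active-minus-placebo differences at the fitted visits and S the within-patient covariance. With complete data, the GLS estimate of the single treatment effect targets w′d, with w = S⁻¹1 / (1′S⁻¹1). Under compound symmetry (the SAP's fallback) the weights are equal whatever the correlation. The share of the Week 12 difference returned is then the plain mean of the onset curve.

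**Assumed inputs** (none is in the documents). Effect at Weeks 1/2/4/8/12 as a percentage of Week 12: slow 10/25/50/80/100, fast 20/45/70/92/100.

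**Share returned, flat SD, compound symmetry**

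| Visits fitted | Slow | Fast |
|---|---|---|
| Weeks 1-12 (skin only) | (10+25+50+80+100)/5 = 53% | (20+45+70+92+100)/5 = 65% |
| Weeks 2-12 | (25+50+80+100)/4 = 64% | (45+70+92+100)/4 = 77% |
| Weeks 4-12 | (50+80+100)/3 = 77% | (70+92+100)/3 = 87% |

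**Share returned, SD rising linearly by visit to 1.5 times from Week 1 to Week 12**, exchangeable or AR(1) correlation 0.3-0.7. Less variable early visits gain weight.

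| Visits fitted | Slow | Fast |
|---|---|---|
| Weeks 1-12 (skin only) | 1-42% | 17-54% |
| Weeks 2-12 | 32-56% | 53-70% |
| Weeks 4-12 | 63-72% | 79-84% |

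The lowest values need strong exchangeable correlation and Week 1 in the model.

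**Power.** Set the Week 12 effect so that a Week 12 contrast has 80% power with 35 per arm, that is, 2.80 standard errors. Under flat SD and exchangeable correlation ρ = 0.5 with k visits, the variance of the common effect relative to the Week 12 contrast is (1 + (k−1)ρ)/k: 0.600, 0.625 and 0.667 for k = 5, 4 and 3. Power ≈ Φ(2.80 × share / √ratio − 1.96). For Weeks 2-12, slow onset: 2.80 × 0.6375 / 0.791 = 2.26, so Φ(0.30) = 62%.

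| Visits fitted | Slow | Fast |
|---|---|---|
| Weeks 1-12 | 48% | 66% |
| Weeks 2-12 | 62% | 78% |
| Weeks 4-12 | 75% | 85% |

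Pooling visits also reduces variance, so power is not always lost.

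**Simulation checks.** In 300 trials per scenario (6 arms of 35, unstructured covariance, ρ = 0.5, no interaction), the shares for Weeks 1-12/2-12/4-12 were 0.52/0.66/0.77 (slow) and 0.66/0.77/0.87 (fast), in line with the formula.

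A second setting assumed Weeks 2-12, SD 5, correlation 0.7 per 4 weeks, an onset of 20/50/80/100% and a true Week 12 difference of −5. The additive model gave −3.15 at every visit. With treatment-by-visit, the estimates at Weeks 2/4/8/12 were −1.00/−2.55/−4.02/−5.04.

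With no effect at any visit (600 trials), the mean estimate was 0.00 and the rejection rate 5.5%, against 4.9% for the Week 12 contrast.

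**The case against.** The strongest reply is that the interaction was plainly meant. Section 7 ties the secondary endpoints to Week 12 and asks for p-values by timepoint, which have little purpose in a model with one common effect. An unstructured covariance is typical of a repeated-measures model described in shorthand. That reading of intent is probably right, but the sentence that lists the terms is complete and the term is absent. Separate ANCOVAs by visit do not fit either, because visit is a fixed effect and a within-patient covariance is specified.

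Redacted blocks follow the model paragraph and might hold more detail. They cannot be counted either way.

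It is fair to say that what is promised is largely within-group LS means, which an additive model can print, though constrained to be parallel. The defect lies in the between-group contrast.

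It also stands that the sizes rest on assumptions, that Week 1 does not apply to DLQI, and that power loss depends on the visit set. With Weeks 4-12 fitted, about 15 of the 24 combinations of SD pattern, correlation and onset curve keep power near 80% or above; the other two sets mostly lose power. The descriptive Week 12 summaries by arm would also make a discrepancy visible.

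None of this supplies the missing term.

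**Conclusion.** The concern holds: the model is wrong as written. Followed literally, it replaces the Week 12 difference for %BSA and DLQI with an average over an unstated set of visits. That result is structural and fails to matter only if the effect is constant over the fitted visits. How much the Week 12 difference is understated depends on the assumed onset curves and covariances and on the visits entered.

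The reach is limited. If there is no effect at any visit, the contrast is centred on zero, so there is no false-positive problem. The primary PASI-75 CMH test, sPGA, the other responder analyses and the sample size are untouched. This should be fixed, but it does not threaten the primary conclusion.

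**What to change.** In SAP Section 7, add treatment-by-visit to the fixed effects (baseline-by-visit is optional). List the post-baseline visits entered for each endpoint. State that each dose-versus-placebo comparison at Week 12 is the contrast of the treatment-by-visit LS means at that visit. Alternatively, specify an ANCOVA of the Week 12 change alone, which is closer to Protocol 10.3.2.

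The cost is one model term and one sentence on visits, with no operational change. Settle the wording before the Week 12 unblinding, because SAP Section 11 has a select group reviewing unblinded Week 12 data before study database lock.
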